10.3.4 Reporting of SAEs

SAE Reporting to the Sponsor via an Electronic Data Collection Tool

- 1. The primary mechanism for reporting a SAE to the Sponsor will be the electronic data collection tool.
- 2. If the electronic system is unavailable for more than 24 hours, then the site will use the paper SAE data collection tool (see below).
- 3. The site will enter the SAE data into the electronic system as soon as it becomes available.
- 4. After the study is completed at a given site, the electronic data collection tool will be taken off-line to prevent the entry of new data or changes to existing data.
- 5. If a site receives a report of a new SAE from a study participant or receives updated data on a previously reported SAE after the electronic data collection tool has been taken off-line, then the site can report this information on a paper SAE form (see next section) or to the Sponsor by telephone.
- 6. Contacts for SAE reporting can be found in Investigator site file.

SAE Reporting to the Sponsor via Paper CRF

- 1. Paper reports via confidential email (pdf) or facsimile transmission of the SAE paper CRF is the preferred method to transmit this information to the Sponsor.
- 2. In rare circumstances if none of the above is available, notification by telephone is acceptable with a copy of the SAE data collection tool sent by overnight mail or courier service.
- 3. Initial notification via telephone does not replace the need for the investigator to complete and sign the SAE CRF pages within the designated reporting time frames.
- 4. Contacts for SAE reporting can be found in Investigator site file.

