8.7.1 Time Period and Frequency for Collecting AE and SAE Information

All AEs will be collected from the signing of the ICF until the EOT visit or end of active follow up.

Medical occurrences that begin before obtaining informed consent will be recorded on the medical history section of the case report form (CRF). Information on major diseases that have occurred in the study subject that might affect function of critical organs (e.g., renal failure, hepatic insufficiency, heart disease) should be collected at screening. Collection of additional clinical history or data that is considered related or appropriate information for study

Page: 54 of 86

intervention/disease under study or deemed relevant by the investigator should also be included.

Medical occurrences that begin before the start of study treatment but after obtaining informed consent will be recorded on the AE section of the case report form (CRF).

Medical occurrences that started before but deteriorated after obtaining informed consent will be recorded as AEs.

All SAEs will be recorded and reported to the Sponsor or designee within 24 hours if investigator awareness, as indicated in Appendix 3. The investigator will submit any updated SAE data to the Sponsor within 24 hours of it being available.

Investigators are not obligated to actively seek AE or SAE in former study participants. However, if the investigator learns of any SAE, including a death, at any time after a participant has been discharged from the study, and he considers the event to be reasonably related to the study treatment or study participation, the investigator must promptly notify the Sponsor.

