- 3. The investigator will use clinical judgment to determine the relationship.
- 4. Alternative causes, such as underlying disease(s), concomitant therapy, and other risk factors, as well as the temporal relationship of the event to study treatment administration will be considered and investigated.
- 5. The investigator will also consult the Investigator's Brochure (IB) and/or Product Information, for marketed products, in his assessment.
- 6. For each AE/SAE, the investigator **must** document in the medical notes that he has reviewed the AE/SAE and has provided an assessment of causality.
- 7. There may be situations in which an SAE has occurred, and the investigator has minimal information to include in the initial report to the Sponsor. However, it is especially important that the investigator always assesses causality for every event before the initial transmission of the SAE data to the Sponsor.
- 8. The investigator may change his opinion of causality in light of follow-up information and send a SAE follow-up report with the updated causality assessment.
- 9. The causality assessment is one of the criteria used when determining regulatory reporting requirements.

Follow-up of AEs and SAEs

- 1. The investigator is obligated to perform or arrange for the conduct of supplemental measurements and/or evaluations as medically indicated or as requested by the Sponsor to elucidate the nature and/or causality of the AE or SAE as fully as possible. This may include additional laboratory tests or investigations, histopathological examinations, or consultation with other health care professionals.
- 2. If a participant dies during participation in the study or during a recognized follow-up period, the investigator will provide the Sponsor with a copy of any post-mortem findings including histopathology.
- 3. New or updated information will be recorded in the originally completed CRF.
- 4. The investigator will submit any updated SAE data to the Sponsor within 24 hours of receipt of the information.

Page: 71 of 86

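### The paper back-up for SAE reports is triggered by an outage of more than 24 hours, a clock not tied to the 24-hour reporting limit, so a site following the rule can report late

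*Protocol*

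**What the plan says.** Protocol section 8.7.1 sets the limit and points to the appendix for the method: "All SAEs will be recorded and reported to the Sponsor or designee within 24 hours if investigator awareness, as indicated in Appendix 3" (the word before investigator is evidently meant to be of). Section 8.7.1 also gives 24 hours for updated SAE data, and section 10.3.3 repeats this: "The investigator will submit any updated SAE data to the Sponsor within 24 hours of receipt of the information".

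Section 10.3.4 gives the method.

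- Item 1 of the electronic procedure: "The primary mechanism for reporting a SAE to the Sponsor will be the electronic data collection tool".
- Item 2, for outages: "If the electronic system is unavailable for more than 24 hours, then the site will use the paper SAE data collection tool".
- Item 3: "The site will enter the SAE data into the electronic system as soon as it becomes available".
- The paper procedure names email or fax as the preferred means and adds: "In rare circumstances if none of the above is available, notification by telephone is acceptable". A telephone call does not release the investigator from the duty to "complete and sign the SAE CRF pages within the designated reporting time frames".

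No instruction covers an SAE whose 24-hour limit will expire before the outage has passed 24 hours.

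**The concern.** Two 24-hour periods stand in the same reporting chain and start from different events. The limit runs from awareness (or, for updates, from receipt). The trigger for paper runs from the start of the system failure. Because the trigger is as long as the limit, the back-up can open after the time it is meant to protect has run out. In a shorter outage it does not open at all.

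What is at stake is the timeliness of safety information. Section 8.7.4 treats prompt SAE notification as essential to legal duties and participant safety. Section 9.6 provides for no data monitoring committee or similar group. The notes to Table 10-1 require possible Hy's Law cases to be reported as SAEs, and the current amendment added newly identified liver-injury findings. Reports of this kind should not wait for an outage to pass a fixed length.

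**Working it through.** The plan gives no figure to reproduce. The check compares the two clocks.

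**Inputs**
- Limit: 24 h from awareness (8.7.1), or 24 h from receipt for updates (8.7.1, 10.3.3).
- Paper trigger: outage longer than 24 h (10.3.4, item 2).
- Otherwise: electronic entry when the system returns (10.3.4, item 3).

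**Set-up.** Awareness is at t = 0 and the deadline at t = 24 h. One continuous outage starts at t = s and lasts d hours. The SAE has not been reported when the outage starts, and the site does what items 1 to 3 direct and no more.

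- If d ≤ 24, paper is never triggered and electronic entry becomes possible at t = s + d.
- If d > 24, paper opens just after t = s + 24.

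In both cases a route opens at about t = s + min(d, 24).

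**Outage starting at or after awareness (0 ≤ s < 24)**
- d > 24: the route opens after s + 24, which is past the deadline for every s ≥ 0.
- d ≤ 24: the report is late whenever s + d > 24, and on time is possible otherwise.
- Worst case: s just under 24 and min(d, 24) = 24, so the route opens at just under 24 + 24 = 48 h, about twice the limit.

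**Outage starting before awareness (s < 0)**
- d > 24: paper opens at s + 24, which is before hour 24, so the limit can be met.
- d ≤ 24: the system is back at s + d, also before hour 24, so the limit can be met.

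**Examples**

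| Outage start s (h) | Length d (h) | Route opens (h) | Against the 24 h limit |
|---|---|---|---|
| −6 | over 24 | after −6 + 24 = 18 | 6 h left |
| 0 | 6 | 0 + 6 = 6 | 18 h left |
| 5 | 23 | 5 + 23 = 28 | 4 h late |
| 10 | over 24 | after 10 + 24 = 34 | more than 10 h late |
| just under 24 | 24 | just under 48 | just under 24 h late |

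For updated SAE data the same arithmetic applies, with receipt of the information at t = 0.

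**The case against.** The best reply is that the sections can be read together. Item 2 says when paper will be used; it does not say that paper may be used only then. The duty in 8.7.1 covers all SAEs and has no outage exception, and the paper procedure itself keeps the reporting time frames in force. A careful site could send paper early and satisfy every sentence. This stands, and it is why a breach is possible rather than built in. It does not make item 2 sound: 8.7.1 sends the reader to the appendix for the method, and the method given there has a waiting period. The contrast with item 5 of the same procedure strengthens the impression that the wait is intended. Once the tool is taken off-line after a site has finished, paper or telephone may be used with no wait.

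Telephone notification is a weaker reply. It is listed within the paper procedure as a last resort, and it leaves the signed pages due on time.

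Four stronger readings might be inferred, and the documents do not support them.

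- That a report is always late when an outage begins at awareness. If the system returns before hour 24, electronic entry can be on time.
- That a site obeying 10.3.4 must violate 8.7.1. Outages that begin before awareness, or end soon enough, leave the limit within reach.
- That partner-pregnancy reports are delayed too. Section 8.7.6 shares the timeline but uses separate pregnancy forms, and nothing shows that these depend on the electronic SAE tool.
- That SAE receipt is the sponsor's only central safety check. Section 8 calls for immediate safety concerns to be discussed with the sponsor at once, 8.7.9 requires immediate contact with the Medical Monitor after an overdose, and 10.3.5 requires the sponsor's medical representative to be told of suspected liver injury as soon as possible.

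**Conclusion.** The point holds in this limited form: item 2 of section 10.3.4 is not linked to the limit in sections 8.7.1 and 10.3.3, and a site that follows it can report late. If the outage starts at or after awareness and lasts more than 24 hours, paper opens only after the deadline. If it lasts 24 hours or less, paper is never triggered, and the report is late whenever the hours already used plus the outage length exceed 24.

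The near-48-hour bound assumes that the site has used almost all its time before the failure and then does nothing beyond items 1 to 3. The documents give no frequency or length of outages, so the expected number of late reports cannot be calculated; in a trial of about 65 participants it is probably small. The consequence is for the timing of safety reports, not for any analysis. The case for changing the text rests on the nature of the duty and the low cost of repair.

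**What to change.** Reconcile 10.3.4 with 8.7.1 and 10.3.3 by replacing item 2 with a rule such as: *Whenever the electronic system is unavailable, the site reports on the paper SAE form so that the sponsor receives the report within 24 hours of awareness (for updated data, within 24 hours of receipt), and enters the data electronically once the system is back.* Carry the same sentence into the investigator site file if the outage rule is repeated there.

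The cost is one sentence and an occasional extra paper form, with later electronic entry of the same data, in short outages. Design, sample size and analyses do not change.

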10.3.5 Identify a potential drug induced liver injury (DILI)

This appendix describes the recommended work up to be followed in order to identify a potential drug induced liver injury (DILI). It is not intended to be a comprehensive guide for the management of elevated liver function tests. During the study the investigator should remain vigilant for increases in liver function tests. The investigator is responsible for determination of the liver function test alterations nature at any point during the study. In case Investigator suspects DILI, the Sponsor Medical Representative has to be informed as soon as possible.

DILI is a diagnosis of exclusion. In case of liver enzyme alterations, please consider the following comprehensive work-up and report results in the eCRF (under "unscheduled visits/unscheduled labs" page):

• Please obtain, and report in the eCRF, a detailed, "liver-focused" medical history including liver metastasis/ liver cancer, alcohol-related liver disease, non-alcoholic steatohepatitis, liver cirrhosis, viral hepatitis, ischemic/congestive hepatic injury, vaccination, biliary obstruction, hemochromatosis, pancreatitis, recent systemic infection/sepsis, COVID-19 Infection, autoimmune disease, alcohol abuse or drug abuse and any other clinically relevant information.

Clinical Study Protocol Global Amendment 1

CONFIDENTIAL BAY 1841788 / 21953 Page: 72 of 86

• Please investigate and report in the eCRF a complete list of concomitant medications, prior chemotherapy or hormonal therapy, antineoplastic drugs, herbal substances, nutritional supplements, complementary and alternative medicines, or exposure to any hepatotoxic agents. Imaging ☐ Abdominal imaging (e.g., Ultrasound, CT, and MRI) Serological tests ☐ Hepatitis A testing: lgM Anti-HAV ☐ Hepatitis B testing: anti-HBc lgG, lgM, HBsAg, HBV DNA ☐ Hepatitis C testing: anti HCV, HCV RNA (PCR) ☐ Hepatitis E testing: anti-HEV (lgG, lgM); HEV RNA ☐ Alcoholic hepatitis: carbohydrate-deficient transferrin ☐ Anti-Cytomegalovirus (CMV) IgM Antibodies ☐ Anti-Epstein Barr Virus (EBV) IgM Antibodies ☐ Herpes Simplex IgG, IgM ☐ Autoantibody and immunoglobulin testing: ANA, ASMA, ANCA, p-ANCA, AMA ☐ Quantitative Ig G, IgM and IgA (optional) ☐ Metabolic disease: Alpha-1-antitripsin, ceruloplasmin, iron, ferritin, GGT, LDH, PT, INR, transferrin, transferrin saturation • Other tests □ PT-INR ☐ Serum albumin ☐ CK Values

☐ Amylase, lipase

Page: 73 of 86

10.4 Appendix 4: Questionnaires10.4.1 FACT-P (Version 4)

FACT-P (Version 4)

Below is a list of statements that other people with your illness have said are important. Please circle or mark one number per line to indicate your response as it applies to the past 7 days.

	PHYSICAL WELL-BEING		A little bit	Some- what	Quite a bit	Very much
091	I have a lack of energy	0	1	2	3	4
092	I have nausea	0	1	2	3	4
069	Because of my physical condition, I have trouble meeting the needs of my family	0	1	2	3	4
094	I have pain	0	1	2	3	4
099	I am bothered by side effects of treatment	0	1	2	3	4
con	I feel ill	0	1	2	3	4
097	I am forced to spend time in bed	0	1	2	3	4
_	SOCIAL/FAMILY WELL-BEING	Not at all	A little	Some- what	Quite a bit	Very
088	I feel close to my friends		1	2	3	4
692	I get emotional support from my family	0	1	2	3	4
0000	I get support from my friends	0	1	2	3	4
084	My family has accepted my illness	0	1	2	3	4
085	I am satisfied with family communication about my illness	0	1	2	3	4
coss	I feel close to my partner (or the person who is my main support)	0	1	2	3	4
qı	Regardless of your current level of sexual activity, please answer the following question. If you prefer not to answer it, please mark this box and go to the next section.					
687	I am satisfied with my sex life	0	1	2	3	4

Seglish (University Deposits 1997, 1997

Page: 74 of 86

FACT-P (Version 4)

Please circle or mark one number per line to indicate your response as it applies to the past 7 days.

_	EMOTIONAL WELL-BEING	Not at all	A little bit	Some- what	Quite a bit	Very much
080	I feel sad	0	1	2	3	4
080	I am satisfied with how I am coping with my illness		1	2	3	4
060	I am losing hope in the fight against my illness	0	1	2	3	4
084	I feel nervous	0	1	2	3	4
065	I worry about dying	0	1	2	3	4
088	I worry that my condition will get worse	0	1	2	3	4
	FUNCTIONAL WELL-BEING	Not at all	A little bit	Some- what	Quite a bit	Very much
orn.	FUNCTIONAL WELL-BEING I am able to work (include work at home)	at all				
OF2		at all	bit	what	a bit	much
	I am able to work (include work at home)	at all 0	bit 1	what	a bit	much 4
OP2	I am able to work (include work at home)	0 0 0	bit 1 1	what	a bit	much 4 4
OP2	I am able to work (include work at home)	0 0 0 0	l 1 1	what	3 3 3	4 4 4
OPS OPS	I am able to work (include work at home) My work (include work at home) is fulfilling I am able to enjoy life I have accepted my illness	0 0 0 0	1 1 1 1	2 2 2 2	3 3 3 3	4 4 4 4

Registe (Universal)
19 November 2001
Page 100 (1977)
Page 2011

Page: 75 of 86

FACT-P (Version 4)

Please circle or mark one number per line to indicate your response as it applies to the past 7 days.

_	_	ADDITIONAL CONCERNS	Not at all	A little bit	Some- what	Quite a bit	Very much
	a	I am losing weight	0	1	2	3	4
	C6	I have a good appetite	0	1	2	3	4
	н	I have aches and pains that bother me	0	1	2	3	4
	P2	I have certain parts of my body where I experience pain	0	1	2	3	4
	273	My pain keeps me from doing things I want to do	0	1	2	3	4
	94	I am satisfied with my present comfort level	0	1	2	3	4
	PS	I am able to feel like a man	0	1	2	3	4
	246	I have trouble moving my bowels	0	1	2	3	4
	97	I have difficulty urinating	0	1	2	3	4
1	86.2	I urinate more frequently than usual	0	1	2	3	4
	PK	My problems with urinating limit my activities	0	1	2	3	4
	BE.5	I am able to have and maintain an erection	0	1	2	3	4

Regish (Universal)
Copyright 1907, 1997
Page 3 of 3

Page: 76 of 86

10.4.2 PROMIS Fatigue

PROMIS® Item Bank v1.0 - Fatigue - Short Form 8a

Fatigue - Short Form 8a

Please respond to each question or statement by marking one box per row.

	During the past 7 days	Not at all	A little bit	Somewhat	Quite a bit	Very much
HI7	I feel fatigued	1	2	3	4	5
AN3	I have trouble starting things because I am tired		2	3	4	5
	In the past 7 days					
FATEXP41	How run-down did you feel on average?	1	2	3	4	5
FATEXP40	How fatigued were you on average?	1	2	3	4	5
FATEXP35	How much were you bothered by your fatigue on average?	1	2	3	4	5
FATIMP49	To what degree did your fatigue interfere with your physical functioning?		2	3	4	5
	In the past 7 days	Never	Rarely	Sometimes	Often	Always
I FATIMP3 I	How often did you have to push yourself to get things done because of your fatigue?		2	3	4	5
I I IFATIMP16	How often did you have trouble finishing things because of your fatigue?	□ 1	2	3	4	5

Page: 77 of 86

10.4.3 PROMIS Physical

PROMIS® Item Bank v2.0 – Physical Function – Short Form 6b

Physical Function - Short Form 6b

Please respond to each question or statement by marking one box per row.

		Without any difficulty	With a little difficulty	With some difficulty	With much difficulty	Unable to do
PEA11	Are you able to do chores such as vacuuming or yard work?	5	4	3	2	1
PFA21	Are you able to go up and down stairs at a normal pace?	5	4	3	2	1
PFA23	Are you able to go for a walk of at least 15 minutes?	5	4	3	2	1
PFA53	Are you able to run errands and shop?	5	4	3	2	1
		Not at all	Very little	Somewhat	Quite a lot	Cannot do
PFC12	Does your health now limit you in doing two hours of physical labor?	5	4	3	2	1
PFB1	Does your health now limit you in doing moderate work around the house like vacuuming, sweeping floors or carrying in groceries?	5	4	3	2	

Page: 78 of 86

10.4.4 Godin-4 questions

The Godin Leisure Time Exercise Questionnaire

INSTRUCTIONS

In this excerpt from the Godin Leisure-Time Exercise Questionnaire, the individual is asked to complete a self-explanatory, brief four-item query of usual leisure-time exercise habits.

CALCULATIONS

For the first question, weekly frequencies of strenuous, moderate, and light activities are multiplied by nine, five, and three, respectively. Total weekly leisure activity is calculated in arbitrary units by summing the products of the separate components, as shown in the following formula:

Weekly leisure activity score = (9 × Strenuous) + (5 × Moderate) + (3 × Light)

The second question is used to calculate the frequency of weekly leisure-time activities pursued 'long enough to work up a sweat' (see questionnaire).

EXAMPLE: Strenuous = 3 times/wk + Moderate = 6 times/wk + Light = 14 times/wk

Total leisure activity score = $(9 \times 3) + (5 \times 6) + (3 \times 14) = 27 + 30 + 42 = 99$

 During a typical 7-Day period (a week), how many times on the average do you do the following kinds of exercise for more than 15 minutes during your free time (write on each line the appropriate number).

a)	STRENUOUS EXERCISE (HEART BEATS RAPIDLY) (e.g., running, jogging, hockey, football, soccer, squash, basketball, cross country skiing, judo,	Times Per Week
b)	roller skating, vigorous swimming, vigorous long distance bicycl MODERATE EXERCISE (NOT EXHAUSTING) (e.g., fast walking, baseball, tennis, easy bicycling,	ing)
	volleyball, badminton, easy swimming, alpine skiing, popular and folk dancing)	
c)	MILD EXERCISE (MINIMAL EFFORT (e.g., yoga, archery, fishing from river bank, bowling, horseshoes, golf, snow-moiling, easy walking)	

During a typical 7-Day period (a week), in your leisure time, how often do you engage in any regular activity long enough to work up a sweat (heart beats rapidly)?

OFTEN SOMETIMES NEVER/RARELY

Page: 79 of 86

10.4.5 Self Efficacy 9 questions

(Resnick et al. 2000)

Self-Efficacy for Exercise (SEE) Scale

About: This scale is a self-report of exercise self-efficacy.

Items: 9

Reliability: Internal consistency = 0.92.

Validity: Mental and physical health scores on the SF-12 predicted efficacy expectations as measured by the SEE Scale. Furthermore, SEE efficacy expectations predicted exercise.

Scoring:

Total score is calculated by summing the responses to each question. This scale has a range of total scores from 0-90. A higher score indicates higher self-efficacy for exercise.

References:

Resnick, B., & Jenkins, L. S. (2000). Testing the Reliability and Validity of the Self-Efficacy for Exercise Scale. *Nursing Research*, 49.

Self-efficacy For Exercise (SEE) Scale

How confident are you right now that you could exercise three times per week for 20 minutes if:

	Not	Con	fiden	t				V	ery C	onfi	dent
The weather was bothering you	0	1	2	3	4	5	6	7	8	9	10
2. You were bored by the program or activity	0	1	2	3	4	5	6	7	8	9	10
You felt pain when exercising	0	1	2	3	4	5	6	7	8	9	10
4. You had to exercise alone	0	1	2	3	4	5	6	7	8	9	10
5. You did not enjoy it	0	1	2	3	4	5	6	7	8	9	10
6. You were too busy with other activities	0	1	2	3	4	5	6	7	8	9	10
7. You felt tired	0	1	2	3	4	5	6	7	8	9	10
8. You felt stressed	0	1	2	3	4	5	6	7	8	9	10
9. You felt depressed	0	1	2	3	4	5	6	7	8	9	10

Page: 80 of 86

